## 9.2.11.2 Best Overall Response Rate

Best overall response rate is calculated the same as the ORR (Section 9.2.11.1), but subjects are summarized at their best response level. Best to worst response is as follows: CR, PR, SD, and then PD.

## 9.2.12 Duration of Response

DOR as measured from the date of first objective response (CR or PR) to date of disease progression or death is documented. DOR data will be censored according to Table 4 for subjects who are alive with no objective documentation of (radiographic) disease progression by the data cut-date.

Table 4 Censoring Rules for Progression-Free Survival

one 4 Censoring Rules for 11 ogression-1	ree Survivar
Situation	Date of Censoring
No baseline radiologic assessment	Date of first study drug dose
No post-baseline radiologic assessment (and no death prior to first scheduled radiologic assessment)	Date of first study drug dose.
No progression or death on study	Date of last radiologic assessment
Documented progression or death after 2 or more consecutive missing radiologic assessments	Date of last radiologic assessment
New anticancer therapy started prior to	Date of last radiologic assessment prior to
progression	new anticancer therapy

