If a patient discontinues study treatment due to the ongoing coronavirus disease 2019 (COVID-19) global pandemic, information should be captured on the eCRF so that this can be summarized in the clinical study report at the end of the study, in line with the FDA Guidance (FDA 2020). The reason for discontinuation should be recorded in the eCRF as COVID-19, if applicable, and include as many details as possible. For example, specific reasons may include, but are not limited to:

- The patient exhibits symptoms consistent with COVID-19.
- The patient has a positive test result for COVID-19.
- The patient has neither symptoms nor a positive test for COVID-19 but has decided to discontinue treatment due to personal choice related to COVID-19 concerns.

Confidential and Proprietary

Patients who are discontinued from study treatment for reasons other than progressive disease by RECIST v1.1 should undergo scans for tumor assessment according to the original tumor assessment schedule (every 8 weeks [± 5 days] from Cycle 1 Day 1) until any of the following occurs, whichever comes first:

- Progressive disease (PD) by RECIST v1.1,
- Initiation of new anticancer treatment, or
- Discontinuation from the study (death, withdrawal of consent, or loss to follow-up).

After discontinuation from study treatment, all patients will have an End-of-Treatment Visit (EOT). All patients, including those discontinued due to PD, will undergo a post-treatment Safety Follow-up Visit at 30 days (± 7 days) after last tarloxotinib infusion.

[figure not shown]
Withdrawal from the study should be in a step-wise fashion. As mentioned above, patients may withdraw or be withdrawn from study treatment. Any patient who withdraws or is withdrawn from study treatment should be encouraged to complete all planned safety and follow-up assessments. If the patient wished to withdraw from all study assessments, permission should be requested to contact the patient, a designated contact person, or the patient's primary care provider. If the patient does not wish any direct follow-up, permission should be requested to conduct periodic medical record review and/or contact the patient's medical care provider.

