- Tarloxotinib infusion (at least 1 hour in duration)
- Concomitant medications
- Assess AEs

Note: Pre-infusion assessments scheduled for Day 1 of Cycles 2 and later cycles are considered Day 29 of the prior cycle. If any patient is not proceeding to an additional cycle, the assessments scheduled for the EOT should be performed within \pm 7 days of their last dose of tarloxotinib.

Every 8 weeks (± 5 days) From Cycle 1 Day 1

- Radiographic tumor assessments
 - The first post-baseline radiographic tumor assessment will occur 8 weeks after the Cycle 1 Day 1 visit. The same imaging modality used for baseline imaging (i.e., CT or MRI) must be used for subsequent radiographic tumor assessments.

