## **6.3.1** Efficacy Assessments

Tumor assessment and imaging was performed according to institutional practice and included computerized tomography (CT) or magnetic resonance imaging (MRI) of the chest and abdomen, brain scan, and bone scan at baseline. The baseline radiographic tumor assessment was required within 28 days prior to the first dose of tarloxotinib, at the Screening assessment. Brain and bone scans did not need to be repeated for subjects with no brain or bone metastases at baseline. Recently completed negative positron emissions tomography (PET) scans could be substituted for baseline bone scans. Subsequent radiographic tumor assessments were every 8 weeks (± 5 days) with respect to Cycle 1 Day 1 (e.g., Cycle 3 Day 1, Cycle 5 Day 1, etc.), until unequivocal PD was documented. The same imaging modality used for baseline imaging (i.e., CT or MRI) was used for subsequent tumor assessments in each subject. In accordance with RECIST v1.1, response (partial response [PR] and complete response [CR]) was confirmed by a second tumor assessment at least 4 weeks after the initial observed response. The scheduling of subsequent tumor assessments may have been adjusted based on the date of the most recent imaging.

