## 9.2.14 Progression-Free Survival

Progression-free survival is defined as the time from the date of first tarloxotinib dose to the date of the first objective documentation of radiographic disease progression or death due to any cause, whichever occurs first. PFS data will be censored according to Table 4 for subjects who are alive with no objective documentation of (radiographic) disease progression by the data cut-date.

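### For a subject with no post-baseline scan who dies between the first and second scheduled scans, SAP Table 4 row 2 censors PFS at first dose, while row 4 (by implication), the lead-in and the PFS definition make the death an event

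*SAP*

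**What the plan says.** SAP 9.2.14 measures PFS from first dose to "the first objective documentation of radiographic disease progression or death due to any cause, whichever occurs first". It then points to the censoring table: "PFS data will be censored according to Table 4 for subjects who are alive with no objective documentation of (radiographic) disease progression". That table is SAP Table 4, printed in 9.2.12; Protocol Table 15 (9.6.2.3) has the same rows.

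Two of the five rows matter here:
- Row 2 covers "No post-baseline radiologic assessment (and no death prior to first scheduled radiologic assessment" and censors at the date of first dose.
- Row 4 covers "Documented progression or death after 2 or more consecutive missing radiologic assessments" and censors at the last scan.

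On timing, SAP 6.3.1 says "Subsequent radiographic tumor assessments were every 8 weeks (± 5 days) with respect to Cycle 1 Day 1", and Protocol 6.9.2 says "The first post-baseline radiographic tumor assessment will occur 8 weeks after the Cycle 1 Day 1 visit".

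SAP 13.3.2 will report Kaplan-Meier PFS by cohort and overall, with medians and 95% confidence intervals. SAP Section 4 lets the SAP govern where it differs from the protocol. No text ranks the rows of the table against each other or against the lead-in.

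**The concern.** Take a subject who stops treatment in Cycle 2, has no on-study scan and dies on Day 75. Row 2 spares only deaths before the first scheduled scan, so it censors this subject at first dose. Row 4 discards a death only after two missed scans, and this subject missed one. The lead-in confines the table to living subjects, and the definition counts any death.

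For a subject with no post-baseline scan, death is the only PFS event possible, because progression must be radiographic. Row 2 removes that event and takes the subject out of the risk set at the start. Two programmers could follow the same plan and report different curves. The cohorts are small (A 11, B 22, C 8), so one subject can shift an estimate visibly.

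**Working it through.** **Scan days.** Eight weeks after Day 1 is 1 + 56 = Day 57, and sixteen weeks is 1 + 112 = Day 113. SAP Table 6 gives the same target days for Cycle 3 Day 1 and Cycle 5 Day 1. With ±5 days the windows are Days 52–62 and 108–118.

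**Classification.** A subject with no post-baseline scan, by day of death:

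| Day of death | Row 2 | Row 4 | Lead-in and definition |
|---|---|---|---|
| Before 57 | Does not apply: event | Event | Event |
| 57 to 113 (118 with window) | Censored at first dose | Event, by implication | Event |
| After the second missed scan | Censored at first dose | Censored at last scan | Event |

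The middle line is the conflict described here. In the last line rows 2 and 4 both remove the death but disagree on the date. The only scan such a subject has is the baseline one, and "The baseline radiographic tumor assessment was required within 28 days prior to the first dose of tarloxotinib". Row 4 would therefore censor up to 28 days before time zero.

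**Size if row 2 is applied.** The plan gives no PFS event count or PFS assumption to reproduce. Let n be the cohort size, k the affected deaths and m the other PFS events by Day 113, with no other censoring before then.
- Row 2 applied: S = 1 − m/(n−k) = (n−k−m)/(n−k)
- Deaths as events: S = 1 − (m+k)/n = (n−k−m)/n
- Ratio: n/(n−k), whatever m is

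For k = 1: Cohort C 8/7 = 1.14; A 11/10 = 1.10; B 22/21 = 1.05; all 41 subjects 41/40 = 1.03.

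**Illustration.** This assumes about 40% of each cohort otherwise has an event by Day 113:

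| Cohort | n | k | m | Row 2 applied | Deaths as events |
|---|---|---|---|---|---|
| A | 11 | 1 | 4 | 1 − 4/10 = 0.60 | 1 − 5/11 = 0.545 |
| B | 22 | 2 | 9 | 1 − 9/20 = 0.55 | 1 − 11/22 = 0.50 |
| C | 8 | 1 | 3 | 1 − 3/7 = 0.571 | 1 − 4/8 = 0.50 |

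**Median.** The median does not follow a fixed ratio. Take Cohort B with k = 2 deaths on Day 85 and the other 20 subjects at exponential quantiles. If the others' assumed median is 112 days, the reported median is 104 days under row 2 and 89 with the deaths as events. If it is 170 days, the figures are 158 and 136. If it is 80 days, they are 74 and 85. Row 2 lowers the curve before the affected deaths and raises it after them, so the median can move either way.

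**The case against.** The strongest reply is that the lead-in settles the matter: the table is for living subjects, so the Day 75 death is an event and nothing is lost. That reading is available, but it cannot simply be presumed. Row 4 expressly censors subjects who progressed or died, and would apply to nobody if the lead-in governed. Row 2's own exception for early deaths would be pointless too.

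A second reply is that the case should be rare. Protocol 5.3 says patients who stop for reasons other than RECIST progression "should undergo scans for tumor assessment according to the original tumor assessment schedule". This stands in part. The rule bites only where a required scan was not done, and the documents do not say how often that happened.

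A third is that little turns on it. PFS is secondary, no efficacy tests are run (SAP 9.1), SAP Section 15 calls the efficacy analyses not interpretable, and SAP 13.3.2 already asks for censoring reasons and a listing. Shifts of 5 to 7 points are also small beside sampling error: exact 95% intervals are about 28–72% for 11/22 and 16–84% for 4/8. All of that limits the importance. It does not remove the contradiction from an estimate that will be reported and, under SAP Section 4, may enter manuscripts.

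A reader might go further and infer that the table removes early deaths generally, or that rows 2 and 4 conflict for every unscanned death after the first scheduled scan. The documents support neither. Deaths before Day 57 stay events, and after two missed scans row 4 censors as well.

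**Conclusion.** The table is wrong as written, in a narrow place: an unscanned subject whose death falls between the first and second scheduled scans. For that subject the governing document gives two incompatible answers.

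If row 2 is followed, Day-113 PFS is overstated by n/(n−k): 1.14, 1.10 and 1.05 for a single death in Cohorts C, A and B. This assumes no other censoring before Day 113. The number of such deaths is not given, and if there were none the effect is zero.

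It would be tempting to conclude that reported PFS is biased upward. The documents do not establish that. It requires at least one such death and a programmer who lets the row override the lead-in. Even then the upward direction is certain for the Day-113 estimate under the stated assumption, but not for the median. No test, sample size or primary result is affected.

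**What to change.** Make the change in the SAP, which governs:
1. In Table 4 row 2, replace the first scheduled scan with the second as the cut-off for death. A death after one missed scan is then an event on the date of death, in line with row 4.
2. State that row 2, with its first-dose date, applies instead of row 4 to later deaths with no post-baseline scan, so that nobody is censored at a pre-dose baseline scan.
3. Reword the lead-in in 9.2.14 so that death or progression is an event except where row 1, 2, 4 or 5 expressly censors it.
4. List any subject whose status changes, and record the departure from Protocol Table 15 in SAP Section 15.

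The cost is a few lines of text and one derivation. The database is already locked, so affected subjects can be identified at once and no new data are needed. The downside is that median PFS may be slightly less favourable.

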#### 9.2.13 Disease Control Rate

Disease control rate is defined as the number of subjects who have CR, PR, or SD for at least 2 cycles (8 weeks) according to the RECIST v1.1 recorded in the period between first study drug dose and disease progression or death to any cause. The DCR on each cohort will be estimated

by dividing the number of subjects with CR, PR, or SD for at least 2 cycles (8 weeks) by the number of subjects enrolled in each cohort.

## 9.2.14 Progression-Free Survival

Progression-free survival is defined as the time from the date of first tarloxotinib dose to the date of the first objective documentation of radiographic disease progression or death due to any cause, whichever occurs first. PFS data will be censored according to Table 4 for subjects who are alive with no objective documentation of (radiographic) disease progression by the data cut-date.

#### 9.2.15 Overall Survival

Overall survival as measured from the date of first tarloxotinib dose to the date of death by any cause. In the absence of confirmation of death, survival time will be censored to last date the subject is known to be alive.

## 9.2.16 Study Drug Exposure Variables

## 9.2.16.1 Total Tarloxotinib Dose (mg) Taken

Total tarloxotinib dosage (mg) is defined as the cumulative dosage of tarloxotinib actually received over the Treatment Period, calculated as follows:

$$Total\ Tarloxotinib\ Dose = \sum_{i=1}^{k} (Actual\ Tarloxotinib\ Dose)_{i}$$

where

 $\Sigma$  represents the summation operator and the value in parentheses is summed over the sequence i = 1 to k, where k = number of tarloxotinib infusions subject received.

## 9.2.16.2 Actual Number of Infusions Administered

The number of infusions a subject received. Interrupted infusions also count as one infusion.

## 9.2.16.3 Actual Number of Cycles Administered

The number of cycles a subject initiated. This includes receiving infusions at each scheduled visit of the cycle (Day 1, Day 8, Day 15, and Day 22).

## 9.2.16.4 Actual Dose Intensity

Actual dose intensity (mg/day) is calculated as total cumulative dose received divided by actual number of infusions administered.

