6.2.3 Tarloxotinib Administration Schedule

Tarloxotinib will be administered on Day 1, Day 8, Day 15, and Day 22 of every 28-day cycle. All infusions after Cycle 1 Day 1 will be administered 7 days \pm 1 day after the prior infusion. Investigators are instructed to avoid dose schedule modifications whenever possible, especially within the first 3 cycles of study treatment. The reason for the dose schedule modification should be recorded in the eCRF.

Dose Delays

All dose schedule modifications of > 1 day must be discussed with the Medical Monitor (or designee). Intentional cycle delays of > 1 day (e.g., patient vacation, physician requested "drug holiday") must be approved by the Medical Monitor (or designee). Study visits will align with tarloxotinib infusion days. If a tarloxotinib dose must be delayed > 3 days, this will be considered a missed dose.

Confidential and Proprietary

Missed Doses

If a patient misses a dose due to hospitalization or any other reason, the next dose received will be referred to as the next scheduled dose (e.g., If a patient misses their Cycle 1 Day 22 infusion, the next dose will be administered at their Cycle 2 Day 1 visit.). If a patient must miss their Cycle 2 Day 1 dose, the assessments that were planned for this visit (e.g. PK assessments and ECGs) should be collected at the Cycle 2 Day 8 visit to ensure adequate data is collected for these endpoints. For other missed visits, any assessments that were part of the missed visit, but are not part of the next visit (i.e., no need to duplicate tests) should be collected, if possible, at the next visit. Radiographic tumor assessments should continue per the Study Schedule (i.e., every 8 weeks [± 5 days] from Cycle 1 Day 1) regardless of changes to the dosing schedule.

If there is an unavoidable delay of an infusion due to COVID-19, the Medical Monitor should be informed as soon as possible. The infusion should be rescheduled based on Investigator judgment, taking into consideration the patient's safety.

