## 9.2.11 RECIST Response Assessment

 Table 3
 Response Evaluation Criteria in Solid Tumours Guidelines

Response assessment	RECIST guideline, version 1.1				
Target lesions					
Complete Response	Disappearance of all target lesions and reduction in the short axis measurement of all pathologic lymph nodes to $\leq$ 10 mm				
Partial Response	≥30% decrease in the sum of the longest diameter of the target lesions compared with baseline				
Progressive Disease	≥20% increase of at least 5 mm in the sum of the longest diameter of the target lesions compared with the smallest sum of the longest diameter recorded OR The appearance of new lesions, including those detected by fludeoxyglucose PET				
Stable Disease	Neither partial response nor progressive disease				
Non-target lesions					
Complete Response	Disappearance of all non-target lesions and normalization of tumor marker levels				
Incomplete Response; Stable Disease	Persistence of 1 or more non-target lesions and/or the maintenance of tumor marker levels above normal limits				
Progressive Disease	The appearance of 1 or more new lesions or unequivocal progression				
If subject has measurable disease, an increase in the overall level or su worsening in non-target lesions, such that tumor burden has increased there is stable disease or partial response in target lesions					

If no measurable disease, an increase in the overall tumor burden comparable in magnitude with the increase that would be required to declare progressive disease in measurable disease (eg, an increase in pleural effusions from trace to large, or an increase in lymphangitic disease from localized to widespread)

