#### 9.2.16.5 Treatment Duration

Treatment duration (days) is defined as (Last Dose Date – First Dose Date + 1 day). Treatment duration indexed by the 28-day cycles is defined as ([Last Dose Date – First Dose Date + 1 day]/28 days), rounded to one decimal place.

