#### 9.3 Analysis Windows

Clinical visits may occur outside protocol-specified windows. Therefore, instead of relying solely on visit labels in the clinical database, analysis visits and their windows are defined using Study Day (See Section 9.2.2). For the purposes of data analysis and summary, assessments and/or measurements will be flagged based on the collection date/time that is closest to the protocol-scheduled time point (or target Study Day). Analysis visit windows are presented in by type of assessments and/or measurements.

**Table 6** Visit Analysis Windows (Clinic visits only)

Protocol Specified Visit	Target Study Day	Start (days)	Stop (days)
Screening	-114	low	-1
Cycle 1 Day 1	1	1	4
Cycle 1 Day 8	8	5	11
Cycle 1 Day 15	15	12	18
Cycle 1 Day 22	22	19	25
Cycle 2 Day 1	29	26	32
Cycle 2 Day 8	36	33	39
Cycle 2 Day 15	43	40	46
Cycle 2 Day 22	50	47	53
Cycle 3 Day 1	57	54	60
Cycle 3 Day 8	64	61	67
Cycle 3 Day 15	71	68	74
Cycle 3 Day 22	78	75	81
Cycle 4 Day 1	85	82	88
Cycle 4 Day 8	92	89	95
Cycle 4 Day 15	99	96	102
Cycle 4 Day 22	106	103	109
Cycle 5 Day 1	113	110	116
Cycle 5 Day 8	120	117	123
Cycle 5 Day 15	127	124	130
Cycle 5 Day 22	134	131	137

Protocol Specified Visit	Target Study Day	Start (days)	Stop (days)
Cycle 6 Day 1	141	138	144
Cycle 6 Day 8	148	145	151
Cycle 6 Day 15	155	152	158
Cycle 6 Day 22	162	159	165
Cycle 7 Day 1	169	166	172
Cycle 7 Day 8	176	173	179
Cycle 7 Day 15	183	180	186
Cycle 7 Day 22	190	187	193
Cycle 8 Day 1	197	194	200
Cycle 8 Day 8	204	201	207
Cycle 8 Day 15	211	208	214
Cycle 8 Day 22	218	215	221
Cycle 9 Day 1	225	222	228
Cycle 9 Day 8	232	229	235
Cycle 9 Day 15	239	236	242
Cycle 9 Day 22	246	243	249
Cycle 10 Day 1	253	250	256
Cycle 10 Day 8	260	257	263
Cycle 10 Day 15	267	264	270
Cycle 10 Day 22	274	271	277
End of Treatment	Treatment End Date	Study Day <= (ADSL.TRTEDT - ADSL.TRTSDT + 1)	
Follow-up	Treatment End Date + 30 Days (± 7 days)	Study Day > (ADSL.TRTEDT - ADSL.TRTSDT + 1)	high

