#### 12 STUDY DRUG AND OTHER MEDICATIONS

#### 12.1 Exposure to Study Drug and Study Treatment Compliance

Summaries of study drug exposure and compliance will be summarized overall and by cohort. The source for study drug dosing and compliance is drug exposure.

The summaries will include total number of cycles initiated, the median (range) of cycles administered, and dose intensity (see definitions in Section 9.2.11) by cohort and overall. The denominators for percentages will be the number of subjects who received the study treatment.

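### SAP dose intensity is labelled mg/day but divides by infusions received, so it is mean mg per infusion and, at a constant dose, cannot register missed or late infusions

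*SAP*

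**What the plan says.** SAP Section 9.2.16.4 gives the definition: "Actual dose intensity (mg/day) is calculated as total cumulative dose received divided by actual number of infusions administered". Its two components are defined just before it:

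- Numerator (9.2.16.1): "Total tarloxotinib dosage (mg) is defined as the cumulative dosage of tarloxotinib actually received over the Treatment Period", written as a sum over the k infusions the subject received.
- Denominator (9.2.16.2): "The number of infusions a subject received. Interrupted infusions also count as one infusion".

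A time variable exists but is not used. Section 9.2.16.5 reads "Treatment duration (days) is defined as (Last Dose Date – First Dose Date + 1 day").

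SAP Section 12.1, on exposure and compliance, says the summaries will include "total number of cycles initiated, the median (range) of cycles administered, and dose intensity (see definitions in Section 9.2.11"). Section 9.2.11 is headed "RECIST Response Assessment"; the exposure variables are in 9.2.16. Protocol Section 9.5 also lists dose intensity, under treatment compliance, without a formula.

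Dosing is once weekly, four infusions per 28-day cycle (SAP Section 6.2.1).

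**The concern.** The unit and the formula do not agree. Milligrams divided by a count of infusions is milligrams per infusion, and with a weekly drug an infusion is not a day. A reader of the table would take mg/day as a delivery rate over calendar time and would overstate that rate several-fold for anyone with more than a few infusions.

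The formula also cannot do the job its placement implies. It sits in the compliance summary, but an infusion that was never given enters neither the numerator nor the denominator, and a late infusion looks the same as a punctual one. The protocol anticipates both without any change of dose:

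- Section 6.2.3 provides for delays and states "If a tarloxotinib dose must be delayed > 3 days, this will be considered a missed dose".
- Section 6.4 delays an infusion for low potassium.
- One row of Table 9 holds treatment for raised transaminases and resumes with no reduction.
- Section 5.3 lets patients who miss two doses continue by agreement.

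It is the only dose-based measure Section 12.1 names. The SAP is meant to support a comprehensive safety analysis and possibly manuscripts (Section 4), where exposure gives the context for adverse-event incidence.

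**Working it through.** The documents report no dose-intensity value, so there is no figure to reproduce. The check is dimensional, followed by worked cases.

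**Inputs.** Dose 150 mg/m² (Protocol Section 6.2.1). Weekly infusions (SAP Section 6.2.1). Target study days from SAP Table 6, where "Cycle 10 Day 22", the 40th weekly infusion, falls on Day 274. Assumption: body surface area 1.8 m², so D = 150 × 1.8 = 270 mg per infusion. The documents give no body surface area; over 1.5 to 2.2 m², D runs from 225 to 330 mg. The ratios and percentages below do not depend on it.

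**SAP formula at constant dose.** kD / k = D = 270 for every k.

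**Unit error, on-time dosing.** The SAP's duration is 7(k − 1) + 1 = 7k − 6 days, so the daily rate is kD / (7k − 6) and the ratio of the SAP value to it is (7k − 6)/k = 7 − 6/k.

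| k | Duration (days) | mg/day on SAP duration | Ratio |
|---|---|---|---|
| 1 | 1 | 270 / 1 = 270 | 1.0 |
| 4 | 22 | 1080 / 22 = 49.1 | 5.5 |
| 8 | 50 | 2160 / 50 = 43.2 | 6.25 |
| 40 | 274 | 10800 / 274 = 39.4 | 6.85 |

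If the last infusion is credited with its own seven days, the rate is kD / 7k = 270 / 7 = 38.6 mg/day and the ratio is 7.0 for every k. Equivalently, 4D / 28 = D / 7 per full cycle.

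**Insensitivity.** The time-based rate in mg/week is total dose / [(last − first + 7) / 7]. The SAP formula gives 270 in every row.

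| History | Last dose day | mg/week | Share of on-time rate |
|---|---|---|---|
| 8 on time | 50 | 2160 / 8 = 270 | 100% |
| 8 at 8-day intervals | 57 | 2160 / 9 = 240 | 89% |
| 7 of 8, miss before last dose | 50 | 1890 / 8 = 236 | 88% |
| 6 of 8, both misses before last dose | 50 | 1620 / 8 = 202.5 | 75% |
| 8 at 10-day intervals | 71 | 2160 / 11 = 196 | 73% |
| 7 of 8, eighth missed | 43 | 1890 / 7 = 270 | 100% |

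The second row lies inside the permitted ±1 day window. The last row shows a limit of any first-to-last-dose rate: doses not given after the final infusion are not counted.

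**What the SAP formula does detect.** Four infusions at 150 then four at 100 mg/m²: (4 × 270 + 4 × 180) / 8 = 225. One half-delivered infusion in eight: (7 × 270 + 135) / 8 = 253.1.

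**The case against.** The strongest reply is that this is one mislabelled descriptive row in an abbreviated report of a terminated study with 41 subjects and no efficacy testing. The formula is printed beside the label, and the number is right if read as mg per dosing day. The limited stakes are accepted. The alternative reading is not: it is still mean dose per infusion, the SAP does not state it, and the next subsection uses days for calendar days.

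Section 12.1 also names cycles administered, which might reflect missed infusions. But Section 9.2.16.3 defines that as cycles initiated and then says it includes infusions at all four visits, so it is unclear whether an incomplete cycle counts, and it is not a dose measure.

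The list in 12.1 is not exhaustive, and total dose, infusion count and treatment duration are presumably defined in order to be reported. That is fair. Infusion count beside duration would show lost delivery, but the SAP does not commit to showing them.

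The illustrations can be called selective. SAP Section 6.2.1 says infusions were given 7 ± 1 days apart, and two missed doses is a discontinuation criterion. However, Protocol Section 6.2.3 counts a dose as missed only beyond a three-day delay, so a 10-day interval is late but not missed, and Section 5.3 contains the exception allowing continuation. The documents give no frequency of either, so the practical size is unknown.

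Finally, mg/week mixes body size with delivery. At 2.0 m² and 75% delivery the rate is 300 × 0.75 = 225, the same as full delivery at 1.5 m². This point stands. It favours a mg/m² or relative measure where the data allow.

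**Conclusion.** The concern holds. Followed as written, Section 9.2.16.4 produces mean mg per infusion under a per-day unit. For punctual weekly dosing the overstatement is sevenfold with the last week credited, or 7 − 6/k on the SAP's duration; for the same number of infusions the ratio is larger when doses are late or are missed between the first and last dose. At a constant dose the value is blind to missed and late infusions; it does respond to dose reductions and partly delivered infusions. The mg values rest on an assumed body surface area of 1.8 m²; the ratios and percentages do not. The dosing histories are illustrative.

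The consequence is a misleading exposure and compliance summary. No decision rule uses the value. It should be corrected, but it does not threaten the study's conclusions.

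**What to change.** In SAP Section 9.2.16.4:

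1. Relabel the present quantity as mean dose per infusion (mg).
2. Define dose intensity (mg/week) = total dose / [(last dose date − first dose date + 7) / 7], and state that doses held after the last infusion are not counted.

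In SAP Section 12.1: list both quantities, with the number of infusions (9.2.16.2) and treatment duration (9.2.16.5), by cohort and overall. Change the cross-reference from 9.2.11 to 9.2.16.

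Optional: add a mg/m²-based or relative dose intensity, which removes the body-size component. This is possible only if the body surface area used for dosing, or height and weight, is in the locked database. Section 9.2.7 derives body mass index from height and weight, but Section 11.3.1 lists only weight, so availability needs checking.

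Cost: SAP wording and one new derived variable, built from dose amounts and dates that 9.2.16.1 and 9.2.16.5 already use. No new data collection and no change to any treatment rule.
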